Appendix V: Risk Assessment and Mitigation Strategy

Potential Risk of Clinical Significance	Data/Rationale for Risk	Mitigation Strategy
Elevated Liver Transaminases (ALT/AST)	Two out of 183 subjects in the Induction Phase of an ongoing study (LAI116482) involving treatment naïve HIV patients receiving oral 744 have developed elevated liver enzymes, considered probably related to oral 744. Both subjects met protocol defined liver stopping criteria and stopped taking oral 744 as a result of these elevations. Transaminases returned to pretreatment levels after stopping drug in both cases. In the two subjects, the peak ALT elevation was greater than 10 times ULN and occurred approximately 4 weeks and 8 weeks, respectively, after initiating daily oral 744 60 mg + ABC/3TC. In both cases the ALT and AST values were elevated while other liver tests remained normal (bilirubin, alkaline phosphatase, albumin). Neither subject developed clinical symptoms of liver dysfunction. No other subjects have required discontinuation of oral 744 as a result of a transaminase elevation. To date, approximately 136 healthy volunteers have received 100-800 mg of 744LA administered as a SC or IM injection. There have been no Grade 3 or Grade 4 ALT elevations while on 744LA. There has been a single subject with a transient Grade 2 ALT elevation following the three monthly injections with 744LA 400 mg that resolved while remaining on 744LA.	Liver transaminases will be closely monitored throughout this study, and liver chemistry stopping criteria will be adopted. All instances of liver transaminase elevations of Grade 2 and above will be followed to resolution. This risk will also be mitigated by exclusion criteria. In addition, an oral lead-in period is being implemented in this study, where all subjects will receive oral 744 for 4 weeks, to determine individual safety and tolerability, prior to the administration of 744LA.

Potential Risk of Clinical Significance	Data/Rationale for Risk	Mitigation Strategy
Injection Site Reactions (ISRs)	The occurrence of injection site reactions (ISRs) was identified in rats and monkeys at all dose levels of 744LA and associated with both the IM and SC route of administration. In humans, experience to date has demonstrated that ISRs occur in the majority of exposed subjects, but are generally mild (Grade 1) and include tenderness, erythema, or nodule formation of several days duration. Reactions to date have been well tolerated and have not to date been associated with subject withdrawal.	Subjects will be closely monitored for ISRs, particularly for signs of pain, tenderness, infections, erythema, swelling, induration, or nodules (granulomas or cysts) throughout the study. Specialist dermatology consultation will be sought if warranted for individual subjects.
Creatine Phosphokinase (CPK) Elevations	Occurrences of asymptomatic, transient instances of elevations of CPK levels have been observed in Phase I studies and an ongoing Phase IIb study with oral 744 at dose levels of 10, 30 and 60 mg (LAI116482). These generally appeared to be related to physical activity, were not associated with clinical symptoms and returned to pre-treatment levels in all cases. No subject has required a discontinuation of GSK1265744 as a result of a CPK elevation. Rhabdomyolysis of uncertain cause has been included in labeling for a currently available integrase inhibitor (raltegravir), but has not been seen in any subject receiving GSK1265744 to date.	Standard laboratory monitoring.
Bone Marrow Depletion	This risk was demonstrated in high dose (1,000 mg/kg/day) oral 744 monkey study, but was not apparent from studies conducted in rats or at lower dose levels in monkeys. Blood disorders such as anemia and leucopenia are labeled for other drugs of the integrase inhibitor class. No signal for bone marrow depletion has been identified to date through Phase IIb.	Doses used within this study will result in many fold lower level exposure compared to the effect level in primates. Careful monitoring of adverse hematological events will occur during study conduct. AEs will be managed appropriately including, but not limited to, withdrawal of 744 (oral or LA), and will be followed to resolution, as per Sponsor's standard medical monitoring practices.

Potential Risk of Clinical Significance	Data/Rationale for Risk	Mitigation Strategy
Gastrointestinal (GI) Intolerability	The risk identified in a monkey toxicity study at the highest administered dose of oral 744 and considered related to local irritation (rather than a systemic effect) leading to morbidity associated with clinical signs of intolerance.	Careful monitoring of adverse GI events will occur throughout the study. AEs will be managed appropriately including, but not limited to, withdrawal of 744, and will be followed to resolution, as per Sponsor's standard medical monitoring practices.
Hypersensitivity Reactions (HSR)	While there have been no clinical cases of hypersensitivity to GSK1265744, there is a theoretical risk of systemic or severe hypersensitivity reactions with or without hepatic symptoms. The long exposures anticipated after a 744LA injection may complicate the management of a drug hypersensitivity reaction, were it to occur.	This risk of developing a hypersensitivity reaction post administration of 744LA will be minimized by the use of an oral 744 lead-in to determine individual safety and tolerability prior to the introduction of 744LA. Any reactions would be managed per standard clinical guidelines.
Drug-Drug Interactions (DDIs)	Residual concentrations of GSK1265744 would remain in the systemic circulation of subjects who stopped treatment (e.g., for tolerability issues or treatment failure) for prolonged periods (months). Subjects discontinuing a 744LA regimen may be at risk for developing DDIs many weeks after discontinuing injectable therapy. Of note, evidence to date indicates that significant DDIs with GSK1265744 and other antiretrovirals are unlikely to occur.	None needed at this time. All subjects will be informed of prohibited medications throughout the study and updates provided as needed to participants.
Development of Resistance in the Setting of HIV Acquisition	Residual concentrations of GSK1265744 would remain in the systemic circulation of participants who stopped 744LA (e.g., for tolerability issues or treatment withdrawal) for prolonged periods (months). Participants discontinuing a 744LA regimen may be at risk for developing resistance to GSK1265744 many weeks after discontinuing injectable therapy were they to become newly infected with HIV.	The risk of HIV acquisition should be minimized in this study on the basis of inclusion of participants at lower risk for acquiring HIV. All participants will be provided HIV counseling and testing throughout the study, as well as provision of condoms and lubricant. Additionally, participants will be followed for 52 weeks from the time of the last injection with 744LA. Participants who acquire HIV on study will be referred for appropriate care.

#### APPENDIX VI: TOXICITY MANAGEMENT

## **Toxicity Management General Guidance**

In general, the IoR has the discretion to hold study product at any time if she/he feels that continued product use would be harmful to the participant, or interfere with treatment deemed clinically necessary according to the judgment of the IoR. In addition, a Clinical Management Committee (CMC) will be established for this study. The CMC's responsibilities will include consultation and decision-making regarding management of toxicities and study product administration, including product resumption following the occurrence of certain types of toxicities and/or permanent discontinuation. Throughout this appendix are examples of AEs that require consultation with the CMC; in all such cases, the CMC should be notified as soon as possible and ideally within 72 hours of site awareness of the AE in question. Investigators also should consult the CMC for further guidance in restarting study product or progressing to permanent discontinuation. Revealing a participant's blinded status will occur only for individuals who become HIV infected and choose to initiate antiretroviral therapy. (A full description of the CMC's role and responsibilities is included in the SSP Manual).

#### Grade 1 or 2

In general, participants who develop a Grade 1 or 2 AE regardless of relatedness to study product, and that is not specifically addressed in the Table below may continue use of the study product per protocol.

#### Grade 3

Participants who develop a Grade 3 AE or toxicity that is not specifically addressed in the Table below and is judged to be related to study product by the Investigator, study product use should be temporarily discontinued in consultation with the CMC. In general, and unless otherwise decided in consultation with the CMC, the investigator should re-evaluate the participant until resolution of the toxicity. The study product should be permanently discontinued if improvement to severity  $\leq$  Grade 2 cannot be documented within 4 weeks of receipt of the initial result. If study product is resumed and the same Grade 3 AE recurs at any time, the Investigator must consult the CMC for further guidance on holding of study product, frequency of reevaluation or progression to permanent discontinuation of the study product.

#### Grade 4

Participants who develop a Grade 4 AE or toxicity that is not specifically addressed below (regardless of relationship to study product) should have the study product temporarily discontinued. The Investigator must consult the CMC and continue the temporary study product hold until a recommendation is obtained from the CMC. In general, study product use will not be resumed if the Grade 4 AE is considered related to study product use. If, in consultation with the CMC, study product use is resumed and the same Grade 4 AE recurs at Grade 4 level at any time, study product must then be permanently discontinued.

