### 2.4 Study Design and Overview

This is a Phase IIa, randomized, multi-site, two-arm, double-blind study of the safety, tolerability, pharmacokinetics, and acceptability of 744LA. Eligible participants will begin an oral lead-in phase in which they will be randomized to receive daily oral 744 (30 mg tablets) or matching placebo for 4 weeks, followed by a one week washout period, to assess safety prior to receiving 744LA. Following final safety lab assessments from the oral regimen phase, participants will enter the injection phase and receive IM injections of 744LA or placebo at three time points at 12 week intervals. IM injections will consist of 800 mg of 744LA or a matching vehicle control, administered as two (2) 400 mg split injections.

176 participants will be randomized 3:1 as follows:

Arm 1: 132 participants will receive daily oral 744 (30 mg tablets) for 4 weeks, followed by a one week washout period, to establish safety and tolerability, followed by intra-muscular (IM) gluteal injections of 800 mg of 744LA (administered as two sequential 400 mg gluteal injections) at three time points at 12 week intervals as: Week 5, Week 17, and Week 29.

Arm 2: 44 participants will receive daily oral matching placebo and IM injections of vehicle-matched placebo on the same schedule as Arm 1.

All participants will receive HIV testing with pre- and post-test counseling, in addition to risk-reduction counseling and condoms and lubricant. All participants will be followed according to the Schedule of Evaluations and Procedures provided in Appendices I-IV.

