# **5.16** Planned Unblinding of Study Participants

When the last participant on the active study product arm completes their Week 41 visit, and when all corresponding procedures at the HPTN SDMC, LC, and LOC have been completed, the study will be unblinded. Participants will be unblinded at their next study visit following final confirmation from the HPTN SDMC that all corresponding unblinding procedures have been completed. Participants in the placebo arm will no longer be required to complete any further follow-up visits once they have been unblinded. Active study product arm participants will complete their follow-up per the appropriate Schedule of Evaluations and Procedures.

As previously noted, due to differences in timing of study initiation across the participating sites, as well as the ratio of active product arm vs. placebo arm participants being enrolled, it is likely that some placebo participants will complete their full follow-up visit schedule.

Additional information will be outlined in the SSP Manual.

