For participants with confirmed HIV infection during follow-up, the treatment assignment will be provided to a subset of the CMC as outlined in the SSP Manual. This is necessary due to the limited information available regarding the study product considering it is investigative in nature,

and this subset of the CMC may assist the site with the appropriate follow-up care, including HIV treatment recommendations.

Sites will have a standard operating procedure (SOP) that outlines a plan in the event that a participant becomes HIV infected during the study, to include the participant's facilitation into immediate suppressive ART treatment to prevent persistent-monotherapy-related resistance complications for a minimum of 52 weeks post-final 744LA injection. At the end of the 52 weeks, participants will be transitioned to a local HIV care clinic where ART provision could be continued (if the participant desires to stay on ART).

Administration of PEP in cases of possible HIV exposure should be expedited at the site level. Such action should be simultaneously and immediately reported to the CMC for assistance with additional clinical and behavioral management plans, as well as decisions about further administration of study medication and follow-up schedules.

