### 7.5 Blinding

Study site staff, with the exception of the site Pharmacist of Record or their designee, and participants will be blinded to the random assignments. Blinding will be maintained until the last participant enrolled in to the active drug arm has completed their Week 41 visit (the time point of the primary endpoint of the study), and when all data related to the Week 41 visit has been entered into the database, as well as cleaned and verified. At a specified time directed by the HPTN SDMC, participants will be unblinded to their treatment assignment, and participants in the placebo arm will no longer need to be followed. Participants in the active study product arm will continued to be followed for 52 weeks after their last injection. In addition, as noted in Section 5.16, an Investigator can request unblinding to the CMC in the event that a participant becomes infected with HIV during the study, and the CMC will assist in the treatment of the participant's HIV infection.

NOTE: Samples may be unblinded in the HPTN Pharmacology Laboratory (only), so the relevant assays are only performed on participants who received the study product.

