#### **Specific Guidance on Transitioning from Oral to Injectable Phases**

Any grade 3 clinical or laboratory AE observed prior to Week 5 will prompt consultation with the CMC prior to any injectable dosing.

Grade 3 adverse events deemed after CMC consultation to clearly not be related to study product may be permissible to continue to injectable dosing provided

- a) Documented resolution to  $\leq$  Grade 1 prior to injectable dosing, and
- b) Approval of the CMC.

Grade 3 adverse events deemed related to study product, or any Grade 4 adverse event will lead to study discontinuation prior to injectable dosing. AE's will be followed until resolution in consultation with the CMC.

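### Minor: Appendix VI, as worded, rules out unblinding one participant for care of a serious adverse event, and its ART-choice condition is not in Sections 5.17 or 7.5

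*Protocol*

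**What the plan says.** Four places in the protocol bear on revealing an individual's assignment.

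- **Appendix VI, Toxicity Management General Guidance.** Revealing a participant's "blinded status will occur only for individuals who become HIV infected and choose to initiate antiretroviral therapy". The next sentence refers to the SSP Manual, but for the role and responsibilities of the CMC.
- **Section 5.17, Follow-up.** "For participants with confirmed HIV infection during follow-up, the treatment assignment will be provided to a subset of the CMC", so that this subset can help the site with follow-up care and HIV treatment. The same section requires site procedures for "facilitation into immediate suppressive ART treatment".
- **Section 7.5, Blinding.** "Study site staff, with the exception of the site Pharmacist of Record or their designee", and participants are blinded. The section adds that, "as noted in Section 5.16, an Investigator can request unblinding to the CMC in the event that a participant becomes infected with HIV".
- **Section 5.16, Planned Unblinding.** This covers only the study-wide unblinding, triggered "When the last participant on the active study product arm completes their Week 41 visit" and the related data procedures are finished.

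**The concern.** A protocol may leave the mechanics of emergency unblinding to a manual. Here the protocol does more than stay silent: it states an exclusive rule, and it does so in the toxicity guidance, where a clinician facing a serious event would look. A site that needed the assignment for a participant's care would have to act against that wording. If the SSP Manual, which is not among the documents, holds an emergency procedure, that procedure would sit uneasily with the rule.

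The protocol gives some reason to want an exception. Holding product does not remove a depot already injected. Section 1.2.4 reports drug detectable for up to 48 weeks after a single injection, and Appendix V warns that prolonged exposure could make a hypersensitivity reaction harder to manage. With 3:1 randomization, 44 of 176 participants (25%) receive placebo, so a clinician cannot take it for granted that drug is present.

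The second, smaller issue is that the sections on HIV infection do not use the same trigger for revealing the assignment.

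**Working it through.** The protocol gives no figure to reproduce. The check is a comparison of texts, followed by a note on how long the rule applies.

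**1. Is there any route to individual unblinding for an adverse event?**

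| Place | What it covers | Route for an adverse event? |
|---|---|---|
| Section 5.16 | Study-wide unblinding after Week 41 | No |
| Section 5.17 | Confirmed HIV infection | No |
| Section 7.5 | HIV infection, on an investigator's request; unblinded assay work in the pharmacology laboratory | No |
| Appendix VI, Grade 4 | Hold product, consult the CMC | No |
| Appendix VI, transition to injections | "Any grade 3 clinical or laboratory AE observed prior to Week 5 will prompt consultation with the CMC" | No |
| Appendix VI, allergic reactions of Grade 3 or higher | If related, stop product permanently and treat | No |
| Appendix VI, general guidance | HIV infection plus choice of ART, exclusively | Excluded |

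Appendix VI also says that participant safety comes first, but that sentence concerns an investigator stopping product before the CMC replies. It does not concern the blind.

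**2. Do the HIV triggers agree?**

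| Place | Trigger | Who learns the assignment |
|---|---|---|
| Section 5.17 | Confirmed infection | Subset of the CMC |
| Section 7.5 | Infection, and the investigator asks | Requested through the CMC |
| Appendix VI | Infection and choice to start ART | Not stated |

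Sections 5.17 and 7.5 can stand together. Appendix VI is the outlier: a participant with confirmed infection who has not chosen ART meets the first trigger, and the second if the investigator asks, but not the third. The Section 7.5 cross-reference is a slip, because Section 5.16 does not mention HIV infection.

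**3. How long does the rule apply?** The blind starts at Week 0: "Eligible participants will begin an oral lead-in phase in which they will be randomized to receive daily oral 744". Accrual is 16 to 24 weeks (Section 7.3), the trigger visit is Week 41, and the third injection is at Week 29. Assume that the first participant enrols at the start of accrual and the last active participant at its end.

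- Last active participant: 41 − 0 = 41 weeks.
- First participant: 16 + 41 = 57 to 24 + 41 = 65 weeks.
- First participant, time since the third injection: 57 − 29 = 28 to 65 − 29 = 36 weeks, which is within the 48 weeks of reported detection.

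Data cleaning would lengthen these periods. Accrual that ends sooner, or placebo assignments at the end of enrolment, would shorten the 57 to 65 and 28 to 36 weeks. They simply restate the length of the blind and do not measure harm.

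**The case against.** The strongest reply is that no clinical decision in this protocol turns on the arm. The hold and stop rules in Appendix VI work blinded. Appendix V calls hypersensitivity a theoretical risk and says reactions would be managed by standard guidelines. This stands, and it is why the point is minor.

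A second reply is that the word *only* cannot be fully literal, since it would then forbid the planned unblinding in Section 5.16. Context must limit it, and the sentence may mean just that the CMC manages toxicity blinded. That reading is possible, but the sentence does not say so, and the CMC is the only channel for individual unblinding that the protocol names.

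A third reply is that the HIV texts can be partly reconciled. Appendix VI names no recipient and could describe disclosure beyond the CMC subset. Because Section 5.17 plans immediate ART, the condition would seldom exclude anyone. This also stands in large part, and leaves a wording mismatch with narrow effect.

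A fourth reply concerns the remedy. The CMC includes the Protocol Chair and site clinicians (Section 6.1) and advises on holds and discontinuations. Releasing assignments through the whole committee would unblind people whose decisions feed the tolerability endpoint in Section 7.1.1. This is right, and the fix must limit who learns the assignment.

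A reader might also infer that the arm could not be found in an emergency, that participants would be harmed, or that the primary results would be biased. The documents support none of these. The Pharmacist of Record knows the assignment, so what is missing is permission to release it. No listed event is treated differently by arm, and no endpoint is shown to depend on this rule.

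**Conclusion.** The point holds as a minor wording defect. Appendix VI states an exclusive rule that, as written, leaves no room for unblinding one participant to care for a serious adverse event, and nothing else in the protocol supplies that room. Its ART-choice condition is absent from Sections 5.17 and 7.5, and the Section 7.5 cross-reference is wrong.

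The frequency of need cannot be estimated from the document and is expected to be low. No effect on any endpoint or estimate is shown. The conclusion rests on the protocol text alone. An emergency procedure in the SSP Manual would reduce the practical risk, but the Appendix VI wording would still need to be brought into line with it.

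**What to change.** 1. In Appendix VI, delete *only* and the ART-choice condition. For HIV, use the Section 5.17 trigger: on confirmed infection, the assignment goes to the CMC subset.
2. Permit documented emergency unblinding when the assignment is needed for a participant's immediate care. The SDMC or the Pharmacist of Record releases it to the treating clinician only.
3. Notify the CMC that an unblinding occurred, but keep the CMC blinded to the assignment except for the designated subset.
4. In Section 7.5, change the cross-reference from Section 5.16 to Section 5.17.

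The cost is a protocol amendment, which Section 10.5 requires to be approved by the relevant IRBs before use, and perhaps a few documented individual unblindings. Limiting release to the treating clinician keeps the rest of the committee that advises on discontinuation blinded.
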